### 7.2.1. Definitions

In determining toxicity grades, the following rules will be applied:

- Worst grades/abnormalities are determined over the entire period (eg, Post-dose 1 or Post-dose 2) separately, including all post-baseline measurements of the corresponding period.
- The abnormalities “abnormally low” and “abnormally high” are considered equally important and both abnormalities are shown in the tables. (This means that the sum of the percentages can exceed 100%).
- If a laboratory value falls within the grading as specified in the grading table but also within the local laboratory normal limits, the value is considered as normal or Grade 0.
- Laboratory results falling between the grading scales will be allocated to the adjacent worst-case grade (because the scale for some parameters in the grading table is not continuous as there may be zones where toxicity grade definitions do not exist).

An abnormality (toxicity grade or abnormality based on normal ranges) will be considered as following vaccination in a period and/or phase if it is worse than the corresponding baseline record. If the baseline value is missing, the abnormality is always considered as following vaccination. A shift from “abnormally low” at baseline to “abnormally high” post-baseline (or vice versa) is also considered as an abnormality following vaccination.

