Upon discharge from the site, subjects will be provided with a diary, a thermometer, and a ruler to measure and record solicited local adverse events and body temperature. Subjects will also record symptoms of solicited local and systemic adverse events in the diary in the evening after vaccination and then daily for the next 7 days. Subjects will be instructed to notify the investigator immediately for any unsolicited adverse event (not listed on the diary card) or for any severe (grade 3) solicited adverse event (listed on the diary card).

Boost Vaccination - Day 29 (Group 1), Day 57 (Group 2), Day 85 (Group 3)

The subjects will receive the boost vaccination via IM injection as described in Section 6, unless any of the pre-specified criteria not to proceed with vaccination are met (see Sections 6.2, 6.3, and 10.2 for details) or if a pause for vaccination of further subjects has been installed (see Section 9.2.3).

Before the boost vaccination, a urine pregnancy test (women of childbearing potential), ECG and vital sign measurements, blood sampling for hematology and chemistry (fasting or non-fasting), and an abbreviated, symptom-directed physical examination (as indicated by the investigator) will be performed.

Blood samples for core immunogenicity assessments in Cohorts II and III will be collected before the boost vaccination as indicated in the [Time and Events Schedule](#) and Section 9.3.2. Blood samples for additional immunogenicity assessments in Cohort II and for specific immunogenicity assessments in Cohort I will be collected as indicated in the [Additional Time and Events Schedule](#) and Section 9.3.2.

The same procedures are applicable as for the prime vaccination regarding vaccine preparation; collection of adverse events, serious adverse events, IREs and pregnancies, together with the information on concomitant therapies; and procedures for subjects after discharging.

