9.1.4. Post-vaccination Phase

The subjects will come to the site at 3 and 7 days after each vaccination and also at 21 and 42 days after the boost vaccination as indicated in the [Time and Events Schedule](#). In Cohorts I and II, the subjects will come to the site for additional post-vaccination visits as indicated in the [Additional Time and Events Schedule](#). The 42-days post-boost visit (Cohorts I and II) may be replaced by a telephone call if the subject is not able to come to the site.

The subject's diary will be reviewed by study-site personnel at 3 and 7 days after each vaccination. The investigator will examine the injection site for occurrences of erythema, induration/swelling, and pain/tenderness, and will ask if itching at the injection site occurred at these visits in order to complete the relevant parts of the CRF.

Blood sampling for hematology and chemistry (fasting or non-fasting) at 7 days after each vaccination and an abbreviated, symptom-directed physical examination (as indicated by the investigator) will be performed. An ECG will be recorded at 7 days after the boost vaccination. Adverse events, serious adverse events and pregnancies will be collected and documented on the CRF, together with the information on any concomitant therapies. For reporting of IREs, refer to Section 12.3.3.

Blood samples for core immunogenicity assessments in Cohorts II and III will be collected as indicated in the [Time and Events Schedule](#) and Section 9.3.2. Blood samples for additional immunogenicity assessments in Cohort II and for specific immunogenicity assessments in Cohort I will be collected as indicated in the [Additional Time and Events Schedule](#) and Section 9.3.2.

Subjects will be instructed to contact the investigator before the next visit (ie, 6 months post-boost) if they experience any adverse event or intercurrent illness that they perceive as relevant and/or can be possibly related to study vaccine in their opinion.

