**Table 2: Analysis Periods**

Phase	Period	Interval	
		From	To
Screening		00:00 on the date of signing the informed consent form	One minute prior to Dose 1 administration on Day 1
Regimen*	Post-dose 1	Date and time of Dose 1 administration	Minimum of: a) 23:59 on the date of last contact (for early study discontinuations) b) 23:59 on the date of relative Day 29 Post-dose 1 c) one minute prior to Dose 2 administration
Post-dose 1 FU		One minute after the end of the Post-dose 1 period	Minimum of: a) 23:59 on the date of last contact (for early study discontinuation or completion) b) one minute prior to Dose 2 administration
Regimen*	Post-dose 2	Date and time of Dose 2 administration	Minimum of: a) 23:59 on the date of last contact (for early study discontinuation or completion) b) 23:59 on the date of relative Day 29 Post-dose 2  Note: subjects who do not receive Dose 2 will not have a Post-dose 2 period.
Post-dose 2 FU		One minute after the end of the Post-dose 2 period	23:59 on the date of last contact (for early study discontinuation or completion)

**Note 1:** \* Regimen period includes both the Post-dose 1 and Post-dose 2 periods.

**Note 2:** FU = follow-up.

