**Table 3: Vaccination Schedules for Sensitivity Analysis**

Group	Group Label (Ad26.ZEBOV, MVA-BN-Filo)	Window (Days)
A	28-day interval	14-42
B	56-day interval	43-70
C	84-day interval	71-98
D	≥99-day interval	≥99

**Note:** the day of the prime vaccination is Day 1

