#### Examples:

Screening phase: start date: 14JUN2016 - stop date: 28JUN2016

Post-dose 1 period: start date: 28JUN2016 - stop date: 26JUL2016

Post-dose 1 FU phase: start date: 27JUL2016 - stop date: 15AUG2016

#### Example for the above Scenario 1

AE1: start date: 20JUN2016- stop date: 10JUL2016

AE2: start date: 08JUL2016- stop date: 18JUL2016

AE1 will be attributed to the Screening Phase and AE2 to the Post-dose 1 period.

#### Example for the above Scenario 3

AE1: start date: 18JUL2016- stop date: 28JUL2016

AE2: start date: 28JUL2016- stop date: 08AUG2016

As AE1 starts in the active period (Post-dose 1) and overlaps with AE2 which starts in a non-active phase (Post-dose 1 FU), this AE is considered as a single AE in the AE analysis starting on 18JUL2016 and ending on 08AUG2016 and is attributed to the Post-dose 1 period.

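### The by-schedule laboratory worst-grade tables draw on one more scheduled blood sample in Group 1 than in Groups 2 and 3 (2 versus 1 in Post-dose 1, 3 versus 2 in Regimen), so a descriptive reading across schedules is tilted against Group 1

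*SAP*

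**What the plan says.** Safety laboratory samples follow the same pattern in every group. After the pre-prime sample there are three scheduled draws. Protocol 9.1.4 provides for "Blood sampling for hematology and chemistry (fasting or non-fasting) at 7 days after each vaccination". Protocol 9.1.3 adds one on the day of the boost: "Before the boost vaccination, a urine pregnancy test (women of childbearing potential), ECG and vital sign measurements, blood sampling for hematology and chemistry". The boost is planned for Day 29, 57 or 85 in Groups 1, 2 and 3 (Protocol 6.1), with a window of one day either side (Protocol Table 3).

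SAP Table 2 closes the Post-dose 1 period at the earliest of last contact and two further limits: "b) 23:59 on the date of relative Day 29 Post-dose 1 c) one minute prior to Dose 2 administration". Time after that and before Dose 2 belongs to a separate follow-up phase. Regimen is Post-dose 1 plus Post-dose 2.

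Within each period, SAP 7.2.1 applies this rule: "Worst grades/abnormalities are determined over the entire period (eg, Post-dose 1 or Post-dose 2) separately, including all post-baseline measurements of the corresponding period". An abnormality "will be considered as following vaccination in a period and/or phase if it is worse than the corresponding baseline record", and the safety baseline is the last value before the prime (Protocol 11.4, SAP 2), so the pre-boost sample counts as post-baseline. SAP 7.2.3 presents the worst abnormalities by regimen and by period or phase, with the focus on Post-dose 1, Post-dose 2 and Regimen.

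**The concern.** A worst-of-several summary rises with the number of samples it is taken over. The planned schedule puts the pre-boost sample inside Post-dose 1 in Group 1 only, and nothing in SAP 7.2 equalises the number of draws or sets that sample apart.

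Until the boost, every active subject has received the same single dose of Ad26.ZEBOV. The Post-dose 1 columns should therefore agree across schedules apart from chance. A surplus in Group 1 could be read as a property of the 28-day schedule when it only reflects an extra blood draw. The schedules are defined by boost timing, and boost timing is what moves the draw in or out of the period, so the artefact lies along the comparison that a reader of these columns would make.

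**Working it through.** **Step 1: the period end.** SAP Table 3 fixes the day numbering: "the day of the prime vaccination is Day 1". The worked example in SAP Attachment 1, Step 2 gives "Post-dose 1 period: start date: 28JUN2016 - stop date: 26JUL2016". 28 June 2016 plus 28 days is 26 July 2016, which is relative Day 29. This reproduces the Table 2 limit. (The Step 1 example stops on 19 July 2016, relative Day 22; it is illustrative and does not alter the rule.)

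**Step 2: scheduled draws per period.** The draws at Day 8, before the boost and 7 days after the boost, placed in the Table 2 periods for a boosted subject:

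| Period | Group 1, boost Day 28 or 29 | Group 1, boost Day 30 or later | Group 2 | Group 3 |
|---|---|---|---|---|
| Post-dose 1 | 2 | 1 | 1 | 1 |
| Post-dose 1 follow-up | 0 | 1 | 1 | 1 |
| Post-dose 2 | 1 | 1 | 1 | 1 |
| Regimen | 3 | 2 | 2 | 2 |

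A subject never boosted has one draw in Post-dose 1 and one in Regimen, in any group. Day 30 is inside the permitted window, so ascertainment also differs within Group 1.

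**Step 3: effect on the rate.** Let p be the chance that one draw shows an abnormality worse than baseline, equal in all groups. For k independent draws, P(at least one) = 1 − (1 − p)^k. The same formula reproduces every cell of Protocol Table 7 to the whole percent (for example N = 121 at 0.5% gives 45%). For two draws with correlation ρ, P = 1 − [(1 − p)² + ρp(1 − p)]. If a fraction f of Group 1 has two draws in the period, the Group 1 rate is f × P + (1 − f) × p. The documents give none of p, ρ or f. Assumed: p from 1% to 30%, ρ of 0 or 0.5, f of 1, 0.5 or 0.25.

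Post-dose 1, Group 1 rate with its ratio to Groups 2 and 3:

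| p (Groups 2 and 3) | ρ = 0, f = 1 | ρ = 0.5, f = 1 | ρ = 0.5, f = 0.5 |
|---|---|---|---|
| 1% | 1.99% (1.99) | 1.50% (1.50) | 1.25% (1.25) |
| 10% | 19.0% (1.90) | 14.5% (1.45) | 12.25% (1.225) |
| 20% | 36.0% (1.80) | 28.0% (1.40) | 24.0% (1.20) |
| 30% | 51.0% (1.70) | 40.5% (1.35) | 35.25% (1.175) |

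For p = 10% and ρ = 0.5: 1 − (0.81 + 0.045) = 0.145; with f = 0.5, 0.5 × 0.145 + 0.5 × 0.10 = 0.1225. With ρ = 0 and f = 0.5 the ratio is 1.50 to 1.35. With ρ = 0.5 and f = 0.25 it is 1.12 to 1.09.

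Regimen, 3 versus 2 independent draws, all subjects boosted and all of Group 1 by Day 29: 2.97% versus 1.99% at p = 1% (ratio 1.49), 27.1% versus 19.0% at 10% (1.43), 65.7% versus 51.0% at 30% (1.29).

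**The case against.** The best defence is that little rests on these tables. Laboratory grades are not among the primary endpoints in Protocol 9.2.1. Clinically relevant laboratory changes are also recorded and analysed as adverse events (SAP 7.2). No formal comparison of schedules is planned (SAP 1.3). Placebo subjects in Cohorts II and III follow the same draw schedule as active subjects in their group, so the within-schedule contrast has equal draws. The Group 2 and 3 pre-boost results are not lost: tables are presented by period or phase, the follow-up phase is one of those, and subjects with abnormal findings are listed. A Day 29 value before Dose 2 is also a genuine safety observation within 28 days of the prime, and removing it could take a Grade 3 result out of a headline table.

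All of this stands, and it limits the importance of the point and shapes the remedy. It does not remove the artefact: a follow-up column or a listing does not equalise Post-dose 1 or Regimen, and readers compare adjacent schedule columns whether or not a test is planned.

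A reader might go further and infer that the tables pooled by dose are biased too. Pooling removes the schedule comparison, and the planned active and placebo numbers are the same in every group (84/6 and 80/24), so Group 1 should contribute about the same share to each pooled arm. A reader might also fault the pre-prime baseline for letting an abnormality already present before the boost count again in Post-dose 2. That baseline is prespecified in both documents and applied alike to all groups and to placebo, so a different reference is a preference and not a correction.

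**Conclusion.** The imbalance is real and follows directly from Table 2 and SAP 7.2.1: 2/1/1 scheduled draws in Post-dose 1 and 3/2/2 in Regimen for Groups 1/2/3 on the planned schedule, with Post-dose 2 balanced. If the true per-draw risk is equal, it raises Group 1's descriptive abnormality rate relative to Groups 2 and 3.

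Its size cannot be fixed from the documents. A doubling is tempting to infer, but a ratio of about 2.0 to 1.7 is an upper limit that needs independent draws and every Group 1 subject boosted by Day 29. Both draws are judged against the same baseline value, so some positive correlation is likely. Protocol 3.2 and SAP 1.4 report many late or absent boosts, and Group 1 subjects so affected have one draw in Post-dose 1. With correlation 0.5 the ratio is 1.50 to 1.35; with only half of Group 1 boosted by Day 29 as well, it is 1.25 to 1.18.

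Nor do the documents support reading this as bias in the primary safety endpoints. The point concerns the between-schedule reading of a descriptive laboratory summary, and at that level it deserves correction.

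**What to change.** In SAP 7.2.3:

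- Keep the period worst-grade tables unchanged as a safety summary, so that no value within the period is lost.
- Add a by-schedule table of laboratory abnormalities by scheduled draw: 7 days post-dose 1, pre-boost, and 7 days post-dose 2.
- State that any between-schedule remark on laboratory safety rests on the 7-day post-dose draws, which are common to all schedules. The scheduled counts compared are then one per group after each dose.
- Footnote the Post-dose 1 and Regimen tables with the number of scheduled draws per group, noting that for Group 1 it depends on whether the boost was given by Day 29.

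The cost is one extra table and a footnote. All the samples are already in the protocol schedule.

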- ^o Prior to study vaccine administration.
- ^p A full physical examination, including height and body weight, will be carried out at screening. At other visits, an abbreviated, symptom-directed examination will be performed as indicated by the investigator.
- ^q A single, 12-lead ECG (supine) after at least 5 minutes rest will be performed and interpreted locally. Additional ECG monitoring may be done at other time points during the study if clinically indicated based on signs and symptoms. If blood sampling or vital sign measurement is scheduled for the same time point as ECG recording, the procedures should be performed in the following order: vital signs, ECG(s), blood draw.
- ^r Includes blood pressure, pulse/heart rate (at rest) and body temperature to be assessed prior to study vaccine administration.
- ^s Subjects will use the subject diary to document solicited local and systemic adverse events (reactogenicity) in the evening after each vaccination and then daily for the next 7 days.
- ^t Pregnancies will be reported from signing of the ICF until the end of the study.
- ^u For reporting of immediate reportable events, refer to Section [12.3.3](#).
- ^v Concomitant therapies must be recorded from screening onwards until 42 days after the boost vaccination. Thereafter, concomitant therapies are only to be recorded if given in conjunction with serious adverse events and immediate reportable events.
- ^w Only including the core immunogenicity assessments. Blood samples will be collected for humoral assays from all subjects in Cohorts II and III and for cellular assays from subjects in Cohorts II and III at selected sites with the capabilities to process PBMC (targeted at 10% of all subjects).
- ^x Subjects who receive the boost vaccination outside the protocol-defined boost vaccination window due to pausing of the study, will only have blood samples taken to assess humoral immune responses measured at selected time points by ELISA. In addition, blood samples will be taken prior to the boost vaccination and at the 7-day post-boost visit for safety assessments.
- ^y For potential additional immunogenicity assessments in Cohort II and specific immunogenicity assessments in Cohort I, see [Additional Time and Events Schedule](#).

ADDITIONAL TIME AND EVENTS SCHEDULE

Cohort I	Vaccination and Post-vaccination Phase ^{a,b}										
	Group 1	Day 1	Day 9	Day 11	Day 13	Day 15	Day 29	Day 32	Day 34	Day 36	Day 38
							Day 57	Day 60	Day 62	Day 64	Day 66

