11.4. Safety Analyses

No formal statistical testing of safety data is planned. Safety data will be analyzed descriptively (including 95% confidence intervals, if applicable), by cohort and overall.

Baseline for all safety parameters will be defined as the last value before the prime vaccination.

Adverse Events (Including Reactogenicity)

The verbatim terms used in the CRF by investigators to report adverse events will be coded using the Medical Dictionary for Regulatory Activities (MedDRA). All reported adverse events (solicited local, solicited systemic, and unsolicited) will be included in the analysis. For each

adverse event, the number and percentage of subjects who experience at least 1 occurrence of the given event will be summarized by group. Summaries, listings, datasets, or subject narratives may be provided, as appropriate, for those subjects who die, who discontinue study vaccine due to an adverse event, or who experience a severe or a serious adverse event.

The analysis for solicited adverse events will be done on those subjects in the Full Analysis set for whom reactogenicity assessments are available in the database. The analysis of unsolicited adverse events will be done on the Full Analysis set.

Clinical Laboratory Tests

Laboratory abnormalities will be determined according to the toxicity grading tables, and in accordance with the normal ranges of the clinical laboratory. The most severe laboratory abnormalities following vaccination will be tabulated per regimen.

Vital Signs and Electrocardiogram

Vital signs and ECG abnormalities following vaccination will be tabulated by most severe abnormality grade.

Physical Examination

Physical examination abnormalities following vaccination will be tabulated by most severe abnormality grade.

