## 2. GENERAL ANALYSIS DEFINITIONS

The type I error rate ( $\alpha$ ) is set to 0.05 and corresponding 2-sided 95% confidence intervals (CIs) will be calculated wherever applicable. Adjustment of the  $\alpha$  (type I error) level due to

multiplicity is not applicable for this study as no planned formal statistical hypothesis testing will be performed.

Analysis and evaluation are defined separately for each parameter later in this document together with the description of rules for handling missing or incomplete data. The analyses will include vaccinated subjects with respect to the actual vaccine administered. The subjects who were vaccinated according to MVA-BN-Filo prime/Ad26.ZEBOV boost or a homologous (ie, Ad26.ZEBOV prime/ Ad26.ZEBOV boost or MVA-BN-Filo prime/MVA-BN-Filo boost) schedule will be excluded from summary analyses (ie, tables and graphs) and listed separately.

In general, the study data will be analyzed as follows:

- Categorical variables will be summarized with a frequency table presenting counts and percentages.
- Continuous variables will be summarized using the following statistics, as appropriate: number of observations, arithmetic mean, geometric mean, corresponding 95% confidence interval (CI), standard deviation, standard error, median, quartiles (Q1 and Q3), minimum and maximum.

*Baseline value* will be defined as the value of the last available assessment performed prior to the prime vaccination, unless specified otherwise.

For safety assessments, the *baseline value* will be an assessment performed prior or on the date (if only time of assessment is missing) of the prime vaccination. The baseline value for immunogenicity assessments will be an assessment performed before or on the date of the prime vaccination. In case of multiple values, the value closest to the vaccination will be used as the baseline.

*Reference value* (only for immunogenicity) will be defined as the assessment performed on the date of the boost vaccination. In case of multiple values (on the same day of vaccination), the value closest to the vaccination will be used as the reference value.

*Visit day* will be determined relative to the actual day of vaccination (date of prime vaccination or date of boost vaccination).

Repeated assessments of immunogenicity and safety will be allocated to analysis windows and periods based on [Table 1](#) and [Table 2](#).

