**7.2.3. Analysis Methods**

Laboratory abnormalities will be determined in accordance with the toxicity grading tables (Attachments 3), and in accordance with the normal ranges of the clinical laboratory. The worst abnormalities following vaccination will be summarized (ie, showing number and percentage) by regimen and presented per period/phase, with special attention to Grade 3 toxicities. Focus will be on clinical abnormalities that occur during Post-dose 1 and Post-dose 2 periods, as well as the Regimen Phase. Similar tables for worst abnormalities will be provided pooled by vaccine (dose). A listing will also be provided for subjects with any abnormal laboratory findings following vaccination.

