**7.4. Electrocardiogram**

Note that a single, 12-lead ECG was performed at screening, pre-boost and 7 days post-boost, and interpreted locally. Additional ECG monitoring could be done at other time points during the study, only if clinically indicated based on signs and symptoms. Therefore, only a listing of subjects with an electrocardiogram abnormality following vaccination will be generated.

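### Post-dose 2 laboratory abnormalities are judged only against the pre-prime value, so changes that arose between prime and boost are tabulated under the boost

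*SAP*

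**What the plan says.** - **Baseline.** SAP 2: the baseline "will be defined as the value of the last available assessment performed prior to the prime vaccination, unless specified otherwise". Section 7.2 specifies nothing different for laboratory data. Protocol 11.4 agrees: "Baseline for all safety parameters will be defined as the last value before the prime vaccination".
- **Rule.** SAP 7.2.1 determines worst grades separately for the Post-dose 1 and Post-dose 2 periods. An abnormality "will be considered as following vaccination in a period and/or phase if it is worse than the corresponding baseline record".
- **Boost-day comparator.** SAP 2 does define a reference value at the boost, but its definition restricts it to one data type: "only for immunogenicity) will be defined as the assessment performed on the date of the boost vaccination".
- **Output.** SAP 7.2.3 tabulates worst abnormalities by regimen and period, with the focus on Post-dose 1, Post-dose 2 and the Regimen phase. It repeats the tables pooled by vaccine dose and adds a listing.
- **Data available.** Protocol 9.1.3 and the Time and Events Schedule place hematology, chemistry and an ECG before the boost injection; 9.1.4 places the next safety draw 7 days later. Footnote x of that schedule keeps both draws for subjects boosted late because of the pause: "In addition, blood samples will be taken prior to the boost vaccination and at the 7-day post-boost visit for safety assessments".
- **ECG.** SAP 7.4: "Note that a single, 12-lead ECG was performed at screening, pre-boost and 7 days post-boost, and interpreted locally". The only ECG output is a listing of subjects with an abnormality after vaccination.

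**The concern.** The Post-dose 2 and by-dose tables are where a reader looks for laboratory changes after MVA-BN-Filo. The comparator, however, predates both vaccines. The tables therefore cannot separate what began after the boost from what was left over from the prime or had drifted in between, although the draw that would separate them is scheduled for every boosted subject.

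The question is a live one. Protocol 1.1.2.2 reports hypokalemia and decreased neutrophils after MVA-BN-Filo (in similar numbers after placebo) and, less often, decreased hemoglobin. Hemoglobin is graded only on change, so the choice of comparator sets the grade itself.

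**Working it through.** **1. Age of the comparator.** Boost days are 29, 57 and 85 (Protocol 6.1), and 99 or later for the delayed category in SAP Table 3. Adding 7 gives Day 36, 64, 92 and at least 106, as in SAP Table 1. With the laboratory baseline drawn on Day 1 before the prime, its age is the visit day minus 1:

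- Group 1: 36 − 1 = 35 days
- Group 2: 64 − 1 = 63 days
- Group 3: 92 − 1 = 91 days
- Boost at Day 99 or later: at least 106 − 1 = 105 days

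With the ±1-day windows on boost and visit, the ranges for Groups 1 to 3 are 33–37, 61–65 and 89–93 days. The pre-boost value would be about 7 days old in every group.

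**2. What the rule does to individual patterns** (G = grade):

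| Pre-prime | Pre-boost | 7 days post-boost | Pre-prime rule, Post-dose 2 | Against pre-boost value |
|---|---|---|---|---|
| normal | G1 | G1 | counted | not counted |
| G1 | G2 | G2 | counted | not counted |
| G1 | normal | G1 | not counted | counted |
| G1 | G1 | G1 | not counted | not counted |
| normal | normal | G1 | counted | counted |

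The first two rows are placed under the boost although they predate it. The third is missed. The fourth shows that a finding unchanged since before the prime is not flagged under either comparator.

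**3. Comparison with the rest of the SAP.** Attachment 1 allocates an unsolicited adverse event to a period by its start date and time. One that began before Dose 2 is therefore not a Post-dose 2 event, while the same persistent finding, as a laboratory value, is. Under SAP Table 2 the Post-dose 1 period ends no later than relative Day 29. In Groups 2 and 3 the pre-boost draw thus falls in Post-dose 1 follow-up, outside the periods of focus, and a finding that arises there and persists first appears in a focus period under Dose 2.

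**4. Illustrative size (assumptions, not from the documents).** Take no vaccine effect, a constant prevalence p of abnormality, correlation r from pre-prime to pre-boost, and s from pre-boost to 7 days after.

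- Flagged under the pre-prime rule: p(1 − p)(1 − rs)
- Of these, already present pre-boost: p(1 − p)(1 − r)[s + p(1 − s)]
- Flagged against the pre-boost value: p(1 − p)(1 − s)

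For p = 0.10, r = 0.2, s = 0.7:

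- Pre-prime rule: 0.09 × 0.86 = 0.0774
- Already present: 0.09 × 0.8 × 0.73 = 0.0526, a share of 0.0526/0.0774 = 68%
- Pre-boost comparator: 0.09 × 0.3 = 0.0270

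In the 164 active recipients per group originally planned in Cohorts II and III, that is 164 × 0.0774 = 12.7 against 164 × 0.0270 = 4.4. Over p = 5–10%, r = 0.2–0.5 and s = 0.3–0.9 the already-present share runs from 20% (p = 5%, r = 0.5, s = 0.3) to 89% (p = 10%, r = 0.2, s = 0.9).

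**The case against.** The pre-prime value is the last unvaccinated state. It is prespecified, and the SAP and protocol agree on it, so nothing is contradictory. This stands, and it is a good reason to keep the pre-prime tables.

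The stakes are limited. Protocol 9.2.1 makes adverse events, serious adverse events, immediate reportable events and solicited events the primary endpoints; laboratory tests and ECGs are other safety assessments. Clinically relevant laboratory worsening is also analysed as an adverse event (SAP 7.2), with allocation by start date. A severe laboratory abnormality judged at least possibly related to the prime, if known in time, already rules out the boost (Protocol 6.3). All of this stands. What remains is mainly lower-grade or unrelated findings, in tables that the SAP nevertheless singles out for attention.

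Placebo recipients face the same rule and visits, so background drift shows up in them too. This stands in part. They were planned at 6 + 24 = 30 per group in Cohorts II and III, and having had no Ad26.ZEBOV they cannot show carry-over from it.

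Two stronger readings are tempting and should not be drawn.

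- **That ECG findings are miscounted under the boost.** The rule quoted above is in the laboratory section, and SAP 7.4 produces only a listing. It is true that the only scheduled pre-prime ECG is at screening, up to 84 days before Day 1 and so up to 84 + 91 = 175 days old in Group 3, but no planned count depends on it.
- **That longer schedules are biased by a stated amount.** Any such figure needs an assumed fall in correlation over time. With 5% prevalence in a bivariate normal model, correlations of 0.6 at 35 days and 0.4 at 91 days give 3.45% and 4.06%. The difference is 0.61 points, about one subject in 164, and it vanishes if the correlation is flat. No formal schedule comparison is planned (SAP 1.3), and the delayed-boost category in SAP Table 3 serves the immunogenicity sensitivity analysis.

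**Conclusion.** The point holds for laboratory data as a weakness of dose attribution. The rule misplaces abnormalities that arose or worsened between prime and boost and persist, and it misses those that were present before the prime, had resolved by the boost and returned at the same grade; it is therefore not simply conservative. The comparator ages (35, 63, 91 and at least 105 days) follow directly from the visit schedule. The 20–89% share rests wholly on assumed prevalence and persistence with no vaccine effect, and shows only that the misplaced part need not be small. The conclusion also assumes that the scheduled pre-boost draws were taken. No primary endpoint is affected. This is an inexpensive improvement, not a flaw that undermines the safety analysis.

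**What to change.** - **SAP 2:** define a second safety comparator, the last value before Dose 2, falling back to the pre-prime value if missing.
- **SAP 7.2.3:** keep all pre-prime tables. Add worst-abnormality tables for the Post-dose 2 period and by vaccine dose that use the new comparator.
- **SAP 3:** record this as an addition to Protocol 11.4, so that it does not become an undeclared departure.
- **SAP 7.4:** in the ECG listing, show the pre-boost result next to the post-boost one.

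The cost is one derived variable and two added table sets, with no new data. The drawback is having two baselines to explain, most visibly for hemoglobin. As an illustration, falls of 1.2 g/dL after each dose total 2.4 g/dL, Grade 3 against the pre-prime value if outside normal limits. The second fall alone is Grade 1 against the pre-boost value. The cumulative change must therefore still be read from the pre-prime and Regimen tables, and a footnote on the new tables should say so.
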